9.2 Vital Signs

- Date of Assessment (listing only)
- Temperature
- Pre- /post-dialysis weight
- Pulse
- Respiratory rate
- Systolic BP
- Diastolic BP

9.3 Clinical Laboratory Evaluations

- Date and time lab sample collected (listing only)
- Initial / re-test (listing only)
- Accession / sample number (listing only)

Table 7: List of Laboratory Tests

(Test on screening pre-dialysis):

- β-hCG (if applicable)
- Hepatitis A, B and C
- Human Immunodeficiency Virus

(Test on screening pre-dialysis, 1st treatment day pre-dialysis, week 4 pre-/post-dialysis and week 24 pre-/post-dialysis):

- λ FLC
- κ FLC

(Test on 1st treatment day pre-dialysis, week 4 pre-/post-dialysis and week 24 pre-/post-dialysis):

- β2-microglobulin
- CFD
- IL-6
- TNFα

(Test on 1st treatment day pre-dialysis, week 12 predialysis, week 24 pre-dialysis and end of study predialysis):

- Factor II
- Factor VII
- Protein C

(Test on 1st treatment day pre-dialysis, week 4 pre-dialysis, week 24 pre-dialysis and end of study pre-dialysis):

• Vitamin A

(Test on every visit pre-dialysis besides end of study pre-dialysis):

• hs-CRP

Serum Chemistry: (Test on every visit pre-dialysis):

• Albumin

(Test on every visit pre-/post-dialysis besides 1st treatment day and end of study):

• BUN

(Test on screening pre-dialysis, 1st treatment day pre-dialysis, week 12 pre-dialysis and end of study pre-dialysis):

• Phosphorus

Coagulation (test on screening pre-dialysis, week 12 pre-dialysis and end of study pre-dialysis):

- Prothrombin time
- INR
- Activated partial thromboplastin time

Comprehensive Metabolic Panel (test on screening pre-dialysis, 1st treatment day pre-dialysis, week 12 pre-dialysis and end of study pre-dialysis):

• Bicarbonate

Hematology (test on screening pre-dialysis, 1st treatment day pre-dialysis, week 12 pre-dialysis and end of study pre-dialysis):

- Calcium
- Chloride
- Creatinine
- Glucose
- Sodium
- Potassium

Liver Function (test on screening pre-dialysis, week 12 pre-dialysis and end of study pre-dialysis):

- Alkaline phosphatase
- ALT; SGPT
- AST; SGOT
- Direct bilirubin
- Gamma-glutamyl transferase
- Globulin
- Total bilirubin
- Total protein

- Hematocrit
- Hemoglobin
- Mean corpuscular hemoglobin
- Mean corpuscular hemoglobin concentration
- Mean corpuscular volume
- Platelet count
- Red blood cell count
- White blood cell count with differential

Lipids (test on screening pre-dialysis, 1st treatment day pre-dialysis, week 12 pre-dialysis and end of study pre-dialysis):

- Total cholesterol
- HDL cholesterol
- LDL cholesterol
- Triglycerides

Note: λ FLC – Lambda Free light chains, κ FLC – Kappa Free light chains, TNF α – Tumor necrosis factor alpha, IL-6 – Interleukin 6, CFD – Complement factor D, hs-CRP – high-sensitivity C-reactive Protein, β -hCG – Beta human chorionic gonadotropin, ALT;SGPT – Alanine aminotransferase; Serum glutamic pyruvic transaminase, AST;SGOT – Aspartate aminotransferase; Serum glutamic oxaloacetic transaminase, BUN – Blood urea nitrogen, HDL – High-density lipoprotein, LDL – Low-density lipoprotein

9.4 Physical Examination

- Examination Date (listing only)
- Weight
- Height (screening only)
- Edema Status (+1, +2, +3, +4)

10. CHANGES IN CONDUCT OR PLANNED ANALYSES FROM THE PROTOCOL

The definition of final measure for laboratory assessments has been updated to the last value captured during study treatment sessions (Week 24). If laboratory assessment in Week 24 is not applicable, the value on end of study visit (pre-dialysis) will be considered as final measurement.

The definition of the per-protocol analysis set has been changed to patients who have received 24 weeks treatment with a study dialyzer, without missing 3 consecutive study treatments (i.e. missing a full week of dialysis); and do not have any major protocol violations that might impact the primary analyses. This update is more in alignment with the expectation of continuous treatment over 6 months period.

For the analyses of adverse events incidences of AEs will be compared between the two treatment groups in addition to the pre-planned analyses based on incidence rates.

In addition to the investigator's assessments of potential abnormal parameters which have been reported as AEs on eCRF, clinical significance will be displayed based on corresponding MedDRA System Organ Class.

The formula for the calculation of the midweek nPNA (nPCR) provided in Appendix 3 of the study protocol was transcribed incorrectly from the source. The correct version of the formula is included in Appendix 1 of this SAP. Safety Parameters

11. SAFETY PARAMETERS

The primary endpoints will be analyzed in a hierarchical manner, starting with the primary safety endpoint.

11.1 Primary Analysis

For the primary safety endpoint of pre-dialysis serum albumin after 24 weeks of treatment, let μ_T denote the Theranova 400 dialyzer pre-dialysis serum albumin mean and let μ_R denote the Elisio-17H dialyzer pre-dialysis serum albumin mean. Then the null hypothesis to demonstrate non-inferiority using a 5% margin can be expressed as:

Ho: μ_T - $\mu_R \leq -1.765$. The alternative hypothesis is expressed as Ha: μ_T - $\mu_R > -1.765$.

An ANCOVA model with fixed effects of treatment and site and the continuous fixed covariate of baseline pre-dialysis serum albumin will be used to generate a two-sided

95% confidence interval (CI) for the difference in treatment means (μ_T - μ_R). If the lower bound is > -1.765 then non-inferiority will be demonstrated.

The primary safety analyses will be performed using a multiple imputation approach. Multiple imputations using SAS Proc MI will be used to impute missing data under the missing at random assumption and the data sets generated will be analyzed using SAS Proc MIANALYZE (for more detail on missing data imputation see Section 7.2.2).

Twenty (20) complete data sets will be analyzed for the multiple imputation of the primary endpoint data.

The analysis of the primary safety endpoint will be carried out on both the FAS and PPS. The analysis using the PPS will be used as a supportive analysis.

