5.2 Baseline Definition

Baseline measure for laboratory assessments and vital signs is defined as the last predialysis non-missing value obtained prior to dialysis on the day of the first study treatment. The final measure for laboratory assessments is defined as the last value captured during study treatment sessions (Week 24). If laboratory assessment on Week 24 is not applicable, the value on end of study visit (pre-dialysis) will be considered as final measurement.

Baseline measure for demographics, physical examination, general medical history and renal medical history is obtained during screening.

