5.3 Sample Size

The sample size for this study is driven by the primary safety endpoint. The sample size calculation was performed using PASS® 15.0.1 software, procedure Non-Inferiority Tests for the difference between Two Means. Copyright© 2017, NCSS, LLC. All Rights Reserved. The power is based on a t-test with a one-sided alpha level of 0.025 where the true difference in means is assumed to be zero (0) and the non-inferiority margin is 5%.

Pre-dialysis serum albumin was not evaluated in the previous Theranova 400 dialyzer HD study, only the mass (G) of albumin in the dialysate was assessed. However, a study published in PLoS ONE⁶ did use a prototype of the Theranova dialyzer (MCO-CI) where in pre-dialysis albumin levels were collected after a month of therapy and, based on these data, a mean and standard deviation (SD) of 35.3 and 3.7 was observed. Comparable pre-dialysis albumin levels are expected with both study dialyzers and with a sample size of 70 patients per group, a t-test with a 0.025 one-sided significance level will have 80% power to demonstrate non-inferiority of the Theranova 400 dialyzer compared to the Elisio-17H dialyzer as assessed by pre-dialysis serum albumin with a non-inferiority margin of 5%. To allow for 15% of patients to drop out, a total of 166 patients will be randomized 1:1 to treatment with the Theranova 400 dialyzer or treatment with the Elisio-17H dialyzer (i.e., 83 patients per group).

A previously conducted Theranova 400 dialyzer prototype HDF study (Comparison of the Clinical Performance of Two Theranova 400 Dialyzer Prototypes in Hemodialysis Mode with the Performance of a High-Flux Dialyzer in Hemodialysis Mode and a High-Flux Dialyzer in High-volume Hemodiafiltration Mode – A Pilot Study, registered at clinicaltrials.gov, NCT02377622) was used to obtain λ FLC reduction ratio mean and standard deviation (SD) of 37.8 and 8.26. With a total sample size of 140 evaluable subjects as determined based on the primary safety endpoint (70 in the Theranova 400 dialyzer treatment group and 70 in the Elisio-17H dialyzer treatment group), a difference of 4.56 in the λ FLC reduction ratio in favor of the Theranova 400 dialyzer can be detected with 90% power at a two-sided 0.05 significance level using a two-sided two-sample t-test assuming equal variances. Including 15% drop out, a total sample size of 166 (83 per treatment group) need to be enrolled into this study.

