7.2.2 Primary Analysis

The primary analyses will be performed using a multiple imputation approach. Multiple imputations using SAS Proc MI will be implemented to impute missing data under the missing at random assumption and the data sets generated will be analyzed using SAS Proc MIANALYZE.⁹

The multiply imputed data sets are then analyzed by using standard procedures for complete data and combining the results from these analyses. Multiple imputation does not attempt to estimate each missing value through simulated values, but rather to represent a random sample of the missing values. This process results in valid statistical inferences that properly reflect the uncertainty due to missing values.

Multiple imputation inference involves three distinct phases:

- 1. The missing data are filled in m times to generate m complete data sets.
- 2. The m complete data sets are analyzed by using standard procedures.
- 3. The results from the m complete data sets are combined for the inference.

The MI procedure is a multiple imputation procedure that creates multiply imputed data sets for incomplete p-dimensional multivariate data. It uses methods that incorporate appropriate variability across the m imputations. The imputation method of choice depends on the patterns of missingness in the data and the type of the imputed variable.

A data set with variables Y_1, Y_2, \ldots, Y_p (in that order) is said to have a monotone missing pattern when the event that a variable Y_j is missing for a particular individual implies that all subsequent variables $Y_k, k > j$, are missing for that individual.

For data sets with monotone missing patterns, the variables with missing values can be imputed sequentially with covariates constructed from their corresponding sets of preceding variables. The regression method (Rubin 1987, pp. 166-167)¹⁰ for imputation will be used. Using the primary safety analysis as an example, if a subject is missing serum albumin values at weeks 20 and 24, a regression model is first fitted using the non-missing values prior to week 20 (baseline, weeks 4, 8, 12, and 16) in order to impute the missing value for week 20. This method is then repeated in order to impute the missing value for week 24 using the non-missing values of the prior weeks plus the newly imputed value for week 20.

Twenty (20) complete data sets will be analyzed for the multiple imputation of the primary endpoint data.

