8. DEMOGRAPHICS AND BASELINE CHARACTERISTICS

Continuous demographic and baseline characteristics including age, height, screening laboratory tests, screening vital signs and renal medical history will be summarized descriptively by treatment group and overall using sample size (N), mean, SD, minimum and maximum. A t-test or Wilcoxon rank-sum test, as appropriate, will be used to evaluate potential differences in the distribution of the underlying demographic or baseline characteristics between treatment groups.

Categorical demographic and baseline characteristics including gender, race, ethnicity, general medical history and renal medical history will be summarized descriptively by treatment group using frequencies and percentages. Treatment group comparability will be evaluated using Fisher's exact test. Medical history, medical condition or surgery items collected on the eCRF will be coded to the appropriate System Organ Class (SOC) and Preferred Term (PT) using the Medical Dictionary for Regulatory Activities (MedDRA), Version 18 or higher.

Information regarding the type and frequency of dialysis therapy received prior to enrollment in this study, and the type of access will be presented. The information gathered will include mean duration of treatments, blood flow rate (Q_B), dialysate flow rate (Q_D) and the type and mean dosage of heparin, erythropoietin and intravenous iron administered.

Relevant medical history for each patient will be obtained during Screening. Medication history, if applicable, will also be evaluated during the Screening period. Past and present conditions, as well as surgical procedures, will be recorded for the main body systems.

Renal medical history, date and type of first chronic dialysis treatment, date of last transplant (if applicable), date of last transplant failure (HD resumed, if applicable), primary renal disease etiology will also be captured in the eCRF. In addition, all medications being taken at Screening and any ESA taken in the 30 days before screening will be recorded.

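### The primary safety ANCOVA is valid but adjusts only for Day 1 albumin; adding the screening albumin already collected is a free gain in precision, modest and of uncertain size

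*SAP*

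**What the plan says.** SAP 11.1 and Protocol 10.5.1 specify the same ANCOVA for Week 24 albumin: "fixed effects of treatment and site and the continuous fixed covariate of baseline pre-dialysis serum albumin". Non-inferiority is met if the lower 95% confidence limit lies above −1.765.

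SAP 5.2 says the laboratory baseline is "defined as the last predialysis non-missing value obtained prior to dialysis on the day of the first study treatment".

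The laboratory schedules (Protocol Appendix 2, SAP Table 2) mark pre-dialysis serum albumin at screening as well as on Day 1, and their notes place all sampling at mid-week sessions. SAP Table 7 agrees: "Serum Chemistry: (Test on every visit pre-dialysis".

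Outside the model, SAP Section 8 gives screening laboratory values a descriptive use: "Continuous demographic and baseline characteristics including age, height, screening laboratory tests, screening vital signs and renal medical history will be summarized". The imputation example in SAP 7.2.2 does not list screening; its regression is "fitted using the non-missing values prior to week 20 (baseline, weeks 4, 8, 12, and 16".

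SAP Sections 12 and 12.1 allow the primary efficacy test only after albumin non-inferiority has been shown.

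**The concern.** One albumin value mixes the patient's underlying level with short-term variation. Protocol 1.2 itself describes albumin as responding to inflammation. Two pre-treatment values will often predict Week 24 albumin better than one, and here both are collected before study treatment at no extra burden.

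Precision matters because the efficacy claim waits on this test. The sample size assumes a true difference of zero, yet Protocol 1.2 says the test dialyzer removes more albumin per session than high-flux dialyzers. If the true mean is slightly lower on Theranova, the width of the interval could decide the result.

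There is a second consequence. The FAS is all randomized patients (SAP 6.2), and randomization takes place at the end of screening (SAP Table 1, note b). A patient randomized but never treated has no day of first study treatment, so the baseline of SAP 5.2 does not exist for that patient, and the imputation sequence has no albumin value to start from. The screening value would supply one.

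**Working it through.** **Inputs from the documents.** SAP 5.3 reports that "a mean and standard deviation (SD) of 35.3 and 3.7 was observed" (read here as g/L, the unit of SAP 5.3.1). The margin is 0.05 × 35.3 = 1.765. One-sided alpha is 0.025, with 70 evaluable patients per group, a true difference of 0 and 15% dropout.

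**The plan's own figure.** SE = 3.7 × √(2/70) = 0.625, and 1.765/0.625 = 2.82. The noncentral t distribution with 138 df gives power 80.0% at 70 per group (the normal approximation gives 80.6%). Dropout: 70/0.85 = 82.4, so 83 per group and 166 in total. The figures reproduce, and they belong to an unadjusted t-test.

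**Formulas.** Let r1 be the correlation of Day 1 with Week 24, r0 that of screening with Week 24, and r that of screening with Day 1.

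- Residual variance as a share of SD², Day 1 only: 1 − r1².
- Both values: 1 − (r1² + r0² − 2·r1·r0·r)/(1 − r²).
- Adjusted SD = 3.7 × √(share). Power is by noncentral t with 70 per group and effect 1.765 minus the true deficit.

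The documents give none of the three correlations, so every value below is an assumption. So are the deficits of 0.5 and 0.75 g/L.

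**One case in full (all correlations 0.6).** Day 1 only: 1 − 0.36 = 0.64, SD 2.96, CI half-width 0.99. Both: 1 − 2 × 0.36/1.6 = 0.55, SD 2.74, half-width 0.92. Ratio 0.55/0.64 = 0.86, a 14% reduction.

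**Range.** Power is shown as Day 1 only → both values.

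| r1 / r0 / r | Variance cut | Deficit 0 | Deficit 0.5 | Deficit 0.75 |
|---|---|---|---|---|
| 0.5 / 0.5 / 0.5 | 11% | 89.9 → 93.0% | 64.0 → 69.1% | 46.1 → 50.6% |
| 0.6 / 0.6 / 0.6 | 14% | 93.9 → 96.6% | 70.9 → 77.3% | 52.2 → 58.4% |
| 0.7 / 0.7 / 0.7 | 17% | 97.5 → 99.1% | 80.3 → 87.0% | 61.7 → 69.7% |
| 0.6 / 0.6 / 0.7 | 10% | 93.9 → 95.8% | 70.9 → 75.3% | 52.2 → 56.5% |
| 0.65 / 0.62 / 0.75 | 7% | 95.8 → 96.9% | 75.3 → 78.2% | 56.4 → 59.4% |
| 0.65 / 0.62 / 0.85 | 2.8% | 95.8 → 96.3% | 75.3 → 76.5% | 56.4 → 57.6% |
| 0.65 / 0.62 / 0.90 | 1.1% | 95.8 → 96.0% | 75.3 → 75.7% | 56.4 → 56.9% |
| 0.60 / 0.54 / 0.90 | 0% | 93.9% | 70.9% | 52.2% |

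The first three rows assume that samples at most 14 days apart correlate no better than samples 24 weeks apart. The fourth relaxes that but keeps screening as good a predictor as Day 1. In the last four, correlation decays with time. The last is the limit in which screening adds nothing beyond Day 1.

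**Checks.** The table ignores site effects. Allowing for 30 sites (about 108 df instead of 138) changes these powers by about 0.2 points or less. Using the mean of the two values gives the same result as entering both when r1 = r0. In the last row it forces equal weights, and residual variance becomes 1 − 0.57²/0.95 = 0.658 against 0.640, about 3% worse than Day 1 alone.

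**The case against.** The strongest reply is that nothing here is wrong. Treatment, site and one baseline covariate make a valid model, specified identically in protocol and SAP, and the gain may be negligible. Samples days apart would ordinarily correlate more closely than samples 24 weeks apart, and at a screening–Day 1 correlation of 0.85–0.90 the decaying case leaves only 1–3% of variance. This stands, and it limits the size of the point. It does not remove it, because the value is already collected.

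Four stronger readings are tempting, and the documents do not support them.

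- **That the test has only 80% power.** That figure is for an unadjusted t-test. The planned Day 1 ANCOVA already gives about 90–98% at zero difference for correlations of 0.5–0.7. The blinded reassessment in SAP 7.3 can also raise the sample size if the pooled SD exceeds 3.7.
- **That the test gates the whole trial.** SAP Section 12 makes primary efficacy conditional on it. SAP 12.3 does not explicitly tie the secondary hierarchy to it.
- **That the screening value is thrown away.** It is summarized descriptively; it is only absent from the model and from the imputation example.
- **That a patient with a lost Day 1 sample has no baseline.** SAP 5.2 speaks of the last non-missing pre-dialysis value, while only one albumin is scheduled before dialysis on Day 1. The wording may already allow a fall-back to screening. It is ambiguous on this, and the clear gap concerns patients never treated.

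**Conclusion.** The concern holds as a free improvement, not as an error or a source of bias. SAP 11.1 leaves a second pre-treatment albumin out of the model. Using it would cut residual variance by about 0–7% in the decaying patterns and by 11–17% under equal correlations of 0.5–0.7, with intermediate patterns in between. In power, that is about 0–3 points at zero difference and about 0–8 points at a true deficit of 0.5–0.75 g/L.

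These sizes rest on assumed correlations and assumed deficits; the documents establish only the SD, margin, sample size and schedule. The starting value for patients randomized but never treated is a separate benefit that does not depend on the correlations. The documents do not say how many such patients to expect.

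**What to change.** Before unblinding:

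1. In SAP 11.1, enter both screening and Day 1 pre-dialysis albumin as covariates, using the available value if the other is missing. Their mean is an acceptable alternative, but entering both is safer, because the mean can lose a little if screening is the weaker predictor.
2. In SAP 7.2.2, put screening albumin first in the imputation sequence, so that patients randomized but never treated have a starting value.
3. Keep Day 1 as the baseline for change scores and shift tables.
4. List the change in SAP Section 10, since Protocol 10.1 and 10.5.1 also fix the baseline and the model.

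No new data are needed. The cost is the SAP wording and at most one model degree of freedom.

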11.2 Sensitivity Analysis

The impact of missing data on the primary safety analyses will be further explored as sensitivity analyses using observed data as well as last observation carried forward.

11.3 Secondary Analysis

The analysis of the secondary safety endpoints will be carried out on the FAS.

Pre-dialysis serum albumin:

A Mixed-effect Model Repeated Measurement (MMRM) model will be used to evaluate differences between treatment groups in the change from baseline in pre-dialysis serum albumin after each four weeks of treatment. The model will include the fixed effect of treatment and visit; the continuous, fixed covariate of baseline measurement; and the random effect of patient.

Pre-dialysis serum albumin will be further categorized at baseline and final measurement into 4 categories: $< 3.5, \ge 3.5-3.9, \ge 4.0-4.4, \ge 4.5$. Shift tables will be generated to cross tabulate the number of patients within each category by treatment.

Pre-dialysis Factor VII, Protein C, Vitamin A, and Factor II:

An MMRM model will be used to evaluate the differences between treatment groups in the change from baseline in pre-dialysis Factor VII, Protein C, Vitamin A, and Factor II after 4 weeks and after 24 weeks of treatment. The model will include the fixed effect of treatment, visit; the continuous, fixed covariate of baseline measurement; and the random effect of patient.

nPNA (nPCR):

An MMRM model will be used to evaluate differences between treatment groups in nPNA(nPCR) collected after each 4 weeks of treatment. The model will include the fixed effect of treatment, visit, and the random effect of patient.

AEs, SAEs, and Product Complaints:

The summary of AEs will include AEs that occur on the day of or after the first study treatment. AEs will be mapped to a Primary SOC and PT according to MedDRA and summarized descriptively by SOC, PT and treatment group. Treatment group comparability in the incidence and incidence rates of adverse events will be evaluated using Fisher's exact test and Wald's method with normal approximation, respectively.¹⁶ AEs that occur prior to 1st day of study treatment will only be listed.

An overview (overall) summary table of all AEs will be generated that includes the total number of AEs, number and percentage of patients with at least one AE, number and percentage of patients with at least one SAE, number and percentage of patients with at least one AE probably associated with study treatment, number and percentage of patients with an AE leading to study discontinuation and number and percentage of patients with an AE leading to death. This summary table will be presented by treatment group and combining both groups (Total).

Furthermore, separate AE summary tables will be provided by SOC and PT for SAEs and AEs leading to study withdrawal. Separate AE summary tables will be provided to show a breakdown of AEs by SOC, PT and

- a. severity (mild, moderate or severe),
- a. relationship to study treatment ("probably related", "possibly related", and "unable to determine" will be categorized as "related to study treatment" while "unlikely related" and "not related" will be categorized as "unrelated to study treatment").

Study dialyzer related product complaints will be summarized descriptively by study dialyzer.

Chemistry and hematology:

Mean differences between treatment groups in the change from baseline to week 24 predialysis measure (if not applicable, end of study pre-dialysis measure will be used) in chemistry and hematology laboratory tests will be analyzed using an ANCOVA with a fixed effect of treatment and a fixed continuous covariate of baseline laboratory value. BUN will be analyzed in the change from pre-dialysis at screening to pre-dialysis after 24 weeks of treatment; further by BUN reduction ratio as compare to from screening to after 24 weeks of treatment.

The Investigator will receive the laboratory results directly from the central laboratory for review and signature. The Investigator will be notified of any laboratory value that is outside of the normal range, as defined by the laboratory. If a clinically significant change from Screening or the previous visit occurs for any laboratory value and results in medical intervention, as judged by the Investigator, the laboratory abnormality will be recorded as an AE on the eCRF. The Clinical Laboratory Evaluations eCRF page will capture and reconcile with the electronic laboratory data transfer, the sample date and time, test accession number, and if the test is an initial or re-test.

In addition to the investigator's assessments of potential abnormal parameters which have been reported as AEs on eCRF, clinical significance will also be displayed based on potential links to specific MedDRA System Organ Classes and Preferred Terms are indicative of abnormalities of lab values as derived by Baxter's Clinical Medical group's discretion.

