12.3 Secondary Analysis

The analysis of the secondary efficacy endpoints will be carried out on the FA.

In order to account for multiplicity, secondary efficacy analyses will be held to a hierarchical assessment and performed in the order outlined below. If the first analysis results in a p-value <0.05, then formal testing will continue to the second analysis. If the second analysis also results in a p-value <0.05, then formal testing will continue to the third analysis, and so on. This method of hierarchical assessment will continue until an analysis results in a p-value > 0.05, i.e., is considered statistically insignificant. This hierarchical approach guarantees that the overall alpha will not exceed 0.05.

- 1. MMRM of reduction ratio of λ FLC
- 2. MMRM of reduction ratio of CFD
- 3. MMRM of reduction ratio of κ FLC
- 4. MMRM of reduction ratio of IL-6
- 5. MMRM of reduction ratio of TNFα
- 6. MMRM of reduction ratio of β 2-microglobulin
- 7. ANCOVA of change in pre-dialysis β 2-microglobulin from baseline to 24 weeks
- 8. MMRM of Kt/Vurea

An MMRM model will be used to evaluate differences between treatment groups in the reduction ratios of λ FLC, CFD, κ FLC, IL-6, TNF α , β_2 -microglobulin after 4 weeks and after 24 weeks of treatment. The model will include the fixed effect of treatment, visit, and the random effect of patient.

An ANCOVA with a fixed effect of treatment and a fixed continuous effect of baseline pre-dialysis β_2 -microglobulin will be used to evaluate differences between treatment groups for the change from baseline in pre-dialysis β_2 -microglobulin after 24 weeks of treatment.

An MMRM model will be used to evaluate differences between treatment groups in Kt/V_{urea} collected after each 4 weeks of treatment. The model will include the fixed effect of treatment, visit, and the random effect of patient.

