13. EXPLORATORY ANALYSES

An MMRM model will be used to evaluate differences between treatment groups in the change from baseline in pre-dialysis serum levels of hs-CRP after each 4 weeks of treatment. The model will include the fixed effect of treatment, visit, as well as the continuous, fixed covariate of baseline measurement and the random effect of patient.

An MMRM model will be used to evaluate differences between treatment groups in the change from first day of treatment in KDQOL-36 and EQ-5D-5L after 12 weeks and after 24 weeks of treatment. The model will include the fixed effect of treatment, visit, as well as the continuous, fixed covariate of screening measurement and the random effect of patient.

Cumulative doses in the utilization for medications (i.e., ESA, anti-hypertensive, iron and phosphate) over 4 weeks intervals across 24 weeks study treatment will be summarized descriptively. An MMRM model will be used to evaluate differences between treatment groups in the change from accumulation of 4 weeks prior to study treatment after 4, 8, 12, 16, 20 and 24 weeks study treatment. The analysis of the exploratory endpoints will be carried out on the FAS.

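### The albumin MMRM is asked for treatment differences every four weeks, but its additive terms give only one visit-averaged difference; the coagulation-factor visits and λ FLC hierarchy item 1 need reconciling

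*SAP*

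**What the plan says.** **Albumin.** SAP 11.3 (and Protocol 10.6.1) evaluates treatment differences in the "change from baseline in pre-dialysis serum albumin after each four weeks of treatment". The terms are stated in full: "The model will include the fixed effect of treatment and visit; the continuous, fixed covariate of baseline measurement; and the random effect of patient". SAP 4.2 and Protocol 2.2 include describing monthly albumin trends among the secondary objectives. Neither document gives a treatment-by-visit term or a visit-specific contrast.

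**Other safety and exploratory models.** SAP 11.3 models "pre-dialysis Factor VII, Protein C, Vitamin A, and Factor II after 4 weeks and after 24 weeks of treatment". SAP 13 models the "change from baseline in pre-dialysis serum levels of hs-CRP after each 4 weeks of treatment" and the "change from first day of treatment in KDQOL-36 and EQ-5D-5L after 12 weeks and after 24 weeks of treatment". These models have the same additive structure with a covariate. For Factor II, Factor VII and Protein C, the sampling list in SAP 9.3 reads "Test on 1st treatment day pre-dialysis, week 12 predialysis, week 24 pre-dialysis and end of study predialysis". Protocol Appendix 2 and SAP Table 2 agree with that list, whereas Protocol 3.2.2 and SAP 5.6 name week 4.

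**Efficacy hierarchy.** Item 1 in SAP 12.3 (and Protocol 10.6.2) is the MMRM of the λ FLC reduction ratio, fitted to weeks 4 and 24: "The model will include the fixed effect of treatment, visit, and the random effect of patient". SAP 5.7 makes week 24 the primary efficacy endpoint and lists the secondary λ FLC endpoint as first day and week 4. The schedules have only a pre-dialysis λ FLC sample on the first day.

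**The concern.** With additive treatment and visit effects, the fitted treatment difference is the same at every visit. For albumin, the stated task and the stated objective both concern the course over time, and this model assumes that the difference between arms has no course. The primary ANCOVA addresses week 24 only, so the MMRM is the planned between-arm inference on weeks 4 to 20. As written, it could not show with a confidence interval when a difference appears.

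Two neighbouring passages raise a related question of what is being estimated. A week-4 difference in the three coagulation proteins cannot be estimated from samples taken at week 12. Item 1 of the hierarchy also combines week 4 with the visit already used for the primary test, so a significant result does not by itself establish a week-4 effect.

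**Working it through.** **1. The plan's own figures (SAP 5.3).** Inputs: albumin SD 3.7, margin 1.765 (5% of 35.3), 70 per arm, one-sided 0.025, true difference 0; λ FLC SD 8.26, difference 4.56.

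- Albumin: SE = 3.7 × √(2/70) = 0.625 and 1.765/0.625 = 2.82. The noncentral t with 138 df gives 80.0% power, as stated.
- λ FLC: SE = 8.26 × √(2/70) = 1.396 and 4.56/1.396 = 3.27. Power is 90.0%, as stated.

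**2. What the additive albumin model estimates.** With complete data at six visits and a random patient effect, the treatment coefficient is the mean of the six visit differences. If they are zero or constant, the coefficient is right at every visit.

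**3. Illustration with a changing difference.** The profile is assumed; the documents give none. Let the deficit grow linearly to half the margin, 1.765/2 = 0.8825 g/L, at week 24. The week-k difference is -0.8825 × k/24, and the mean is -0.8825 × (1+2+3+4+5+6)/36 = -0.8825 × 0.583 = -0.51.

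| Week | True difference | Reported | Deficit is |
|---|---|---|---|
| 4 | -0.15 | -0.51 | overstated by 0.37 |
| 8 | -0.29 | -0.51 | overstated by 0.22 |
| 12 | -0.44 | -0.51 | overstated by 0.07 |
| 16 | -0.59 | -0.51 | understated by 0.07 |
| 20 | -0.74 | -0.51 | understated by 0.22 |
| 24 | -0.88 | -0.51 | understated by 0.37 |

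With 15.7% uniform monotone dropout (26/166), the reported value is about -0.49. Such a trial would still show non-inferiority in about 37-65% of cases (assumed baseline correlation 0.5-0.8), so the example is not confined to trials that fail the primary test.

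**4. Precision of per-visit albumin estimates.** Assume a common correlation r between any two albumin values, baseline included. Conditional on baseline, the variance is proportional to 1 - r² at one visit and to [(1 - r²) + 5(r - r²)]/6 for the six-visit average.

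- r = 0.5: 0.75 against 0.333, SE 0.54 against 0.36, ratio 1.50.
- r = 0.8: 0.36 against 0.193, SE 0.38 against 0.27, ratio 1.36.

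**5. Item 1, λ FLC.** The first-day reduction ratio cannot be calculated without a post-dialysis sample, so week 4 is the only listed secondary visit that can be analysed. The two-visit average has SE 1.396 × √((1+r)/2), which is 1.13 at r = 0.3 and 1.32 at r = 0.8 (assumed range).

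| Week-4 difference (week 24 = 4.56) | Average | Power, average (r = 0.3 to 0.8) | Power, week 4 alone |
|---|---|---|---|
| 4.56 | 4.56 | 98% to 93% | 90% |
| 2.28 | 3.42 | 86% to 73% | 37% |
| 0 (limiting case) | 2.28 | 52% to 40% | 5% |

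The figures for the average are power for a true non-zero average, not type I error.

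**The case against.** **A visit average may be what is meant.** For the other reduction ratios, and for Kt/V and nPNA, which are "collected after each 4 weeks of treatment", one overall difference is a fair reading. The wording for the coagulation factors, Vitamin A, hs-CRP, KDQOL-36 and EQ-5D-5L is nearly the same, so that reading is possible there too. This stands. Albumin differs because a separate objective on monthly trends supports the by-visit reading.

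**Trends can be described without a model.** SAP 9 and 9.3 point to laboratory values tabulated by arm and visit and/or listed. This also stands in part: what is missing is a planned between-arm difference with a confidence interval at each visit.

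**A reader might infer that the model hides a safety signal, reporting only 58% of the week-24 deficit.** The documents do not support this. The primary ANCOVA in SAP 11.1 estimates week 24 directly, and in the linear example the average overstates the deficit at weeks 4 to 12. The largest understatement that the primary analysis does not cover is 0.22 g/L, about 12% of the margin (0.22/1.765).

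**A reader might also infer that item 1 inflates the type I error, or that it must become a week-4 test.** Neither follows. Item 1 is a valid test of an average in a fixed sequence. SAP 12.3 and Protocol 10.6.2 both specify weeks 4 and 24, so correcting the endpoint list would resolve the conflict equally well. With one dialyzer per patient and prescriptions to be kept stable (Protocol 3.4 and 5.3), similar differences at the two visits are plausible, and the practical effect would then be small.

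**Conclusion.** The concern holds for albumin. The stated target and objective call for differences by visit, and the stated terms cannot supply them. The size depends wholly on how the difference changes with time, which the documents do not give. It is nil under their assumption of zero difference, and at most 0.22 g/L of understatement before week 24 in the linear example.

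For the other models that name visits, the missing interaction is an ambiguity rather than a clear error. The coagulation-factor visit is a plain contradiction: week 4 is to be analysed and week 12 is sampled. Item 1 is an unreconciled difference between the endpoint list and the analysis. It matters for what a significant result may be said to show, not for error control. Both primary analyses, the sample size and the alpha control stand as planned.

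**What to change.** - **Albumin (SAP 11.3, Protocol 10.6.1):** add treatment-by-visit and baseline-by-visit. Report the difference with a 95% CI at each sampled visit, alongside the visit average. This needs no new data. Per-visit intervals are about 36-50% wider than the interval for the average (assumed correlation 0.8-0.5), and the average remains available from the same fit.
- **Other models that name visits (SAP 11.3 and 13):** the same term can be added to the coagulation-factor, Vitamin A, hs-CRP, KDQOL-36 and EQ-5D-5L models without further data. Otherwise, state that the visit average is the intended contrast.
- **Coagulation factors:** reconcile week 4 in SAP 5.6 and 11.3 and Protocol 3.2.2 and 10.6.1 with week 12 in SAP Table 2 and 9.3 and Protocol Appendix 2.
- **Item 1:** reconcile SAP 5.7 with SAP 12.3, and likewise Protocol 3.2.2 with 10.6.2. State before database lock whether the week-4 contrast or the average of weeks 4 and 24 supplies the p-value. If it is the average, say that it does not by itself establish a week-4 effect. If it is week 4, item 1 power under a constant 4.56 difference falls from 93-98% to 90%; item 1 gates items 2 to 8, so that loss of 3 to 8 points carries down the sequence.
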